9.1 Adverse Events

All adverse events will be coded by System Organ Class (SOC) and Preferred Term (PT) according to the Medical Dictionary for Regulatory Activities (MedDRA). AEs that are sexspecific, e.g., ovarian cancer, will have their incidence rates evaluated for the specific sex.

Treatment-emergent AEs (TEAEs) are defined as AEs with an onset date on or after the first dose of IMP. In more detail, TEAEs are all adverse events which started after start of IMP; or if the event was continuous from baseline and was worsening, serious, study drug related, or resulted in death, discontinuation, interruption or reduction of study therapy. Adverse events occurring up to 21 days after the last day of IMP will be included in the summary tables.

The incidence of the following events in the open-label treatment phase will be summarized using the Safety Sample:

- a) TEAEs
- b) TEAEs by severity
- c) TEAEs potentially causally related to the IMP
- d) TEAEs with an outcome of death
- e) Serious TEAEs
- f) TEAEs leading to discontinuations of the IMP

The above summaries (b), (e) and (f) will also be prepared for TEAEs potentially causally related to the IMP.

In addition, incidence of TEAE during the open-label treatment phase of at least 5% by SOC and PT will be provided.

Incidence of TEAEs by SOC and PT will be summarized for sex, race, age and region subgroups.

EPS-related AEs will be grouped into five categories.

- 1) Dystonic Events, which include cervical spasm, dystonia, emprosthotonos, muscle contractions involuntary, muscle rigidity, muscle spasms, muscle spasticity, myotonia, nuchal rigidity, oculogyration, opisthotonos, pleurothotonus, risus sardonicus, torticollis, and trismus;
- 2) Parkinsonian Events, which include akinesia, asterixis, athetosis, bradykinesia, cogwheel rigidity, essential tremor, extrapyramidal disorder, freezing phenomenon, gait festinating, hyportonia, hypokinesia, hypokinesia neonatal, intention tremor, masked facies, parkinson's

Confidential - Proprietary Information

disease, parkinsonian crisis, parkinsonian gait, parkinsonian rest tremor, parkinsonism, tremor, and tremor neonatal;

- 3) Akathisia Events, which include akathisia, hyperkinesia, and psychomotor hyperactivity;
- 4) Dyskinetic Events, which include ballismus, buccoglossal syndrome, choreoathetosis, clumsiness, dyskinesia, dyskinesia neonatal, dyskinesia oesophageal, fumbling, nodding of head, on and off phenomenon, and tardive dyskinesia;

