- 5) Residual Events, which include chorea, huntington's chorea, muscle twitching, and myoclonus.

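### SAP 9.1 splits chorea, athetosis and choreoathetosis across three EPS categories and counts two non-specific overactivity terms as akathisia: a minor correction to a supportive summary

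*SAP*

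**What the plan says.** SAP 9.1 states that "EPS-related AEs will be grouped into five categories" and defines each category by a list of terms. Three entries matter for the first part of this point:

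- Category 2: "Parkinsonian Events, which include akinesia, asterixis, athetosis, bradykinesia, cogwheel rigidity", and further terms.
- Category 4: "Dyskinetic Events, which include ballismus, buccoglossal syndrome, choreoathetosis, clumsiness, dyskinesia", and further terms, among them tardive dyskinesia.
- Category 5: "Residual Events, which include chorea, huntington's chorea, muscle twitching, and myoclonus".

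Category 3 reads in full: "Akathisia Events, which include akathisia, hyperkinesia, and psychomotor hyperactivity". The Parkinsonian list also contains the run "gait festinating, hyportonia, hypokinesia", whose middle word is not a recognisable term.

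The visible text gives no source or rationale for the allocation, and no rule for telling mania-related overactivity from akathisia. The primary analysis does not use these categories: SAP 9 makes it the frequency and severity of adverse events, and SAP 9.1 codes events by system organ class and preferred term.

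**The concern.** The lists are the definition of each category, so a subject is counted wherever the coded term happens to sit. Choreoathetosis names a combination of chorea and athetosis. The SAP treats the combination as dyskinetic and each component as something else, so similar involuntary movements can be counted in three places depending on the word the site used. Anyone reading the Dyskinetic line as the count of such movements over 26 weeks could see too few.

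The Akathisia category has only three terms, and two of them describe overactivity in general. Overactivity can also belong to mania; that is general clinical knowledge, not something the documents state. The subjects all have bipolar I disorder and enter from three-week trials in which the drug was being developed for acute mania (protocol 2.1, 2.2 and 3.1). The akathisia figure could therefore include some events that reflect the illness.

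**Working it through.** There is no sample-size or power figure to reproduce: SAP 4 says that the sample size does not rest on power. The check is of the lists themselves, plus one scale calculation.

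**1. Count of terms (SAP 9.1).** Dystonic 15, Parkinsonian 21, Akathisia 3, Dyskinetic 11, Residual 4. Total 15 + 21 + 3 + 11 + 4 = 54. All 54 are distinct and none appears in two categories, so a subject coded only to chorea or athetosis cannot also be counted as Dyskinetic.

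**2. Where the three movement terms sit.**

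| Term | Category |
|---|---|
| athetosis | Parkinsonian |
| choreoathetosis | Dyskinetic |
| chorea | Residual |

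**3. What moving them would change.** Because all five categories are EPS-related, moving chorea or athetosis changes two category counts, by at most one each per subject. It leaves unchanged the number of subjects with any listed term, and every preferred-term count.

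**4. Scale.** One subject as a percentage of N is 100/N. The documents give no event rates and no Safety Sample size, so both denominators are assumptions taken from protocol 3.3.1.

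- Planned enrolment, N = 384: 100/384 = 0.26 percentage points.
- Target completers, N = 175: 100/175 = 0.57 percentage points.

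As a hypothetical case, take three subjects with one of the three terms each. As listed, the Dyskinetic line shows 1/384 = 0.26%. With the terms together it shows 3/384 = 0.78%.

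**5. The word *hyportonia*.** Every list is alphabetical except the Parkinsonian one, which breaks only at this word. It stands after *gait festinating* and before *hypokinesia*. *Hypertonia* restores the order there; *hypotonia* does not, since it would follow *hypokinesia neonatal*. Neither spelling occurs elsewhere in the lists. If the misprint is in the source file and the list were matched literally to coded terms, the intended term would match nothing. That would lower the Parkinsonian count, and also the count of subjects with any EPS term for those who have no other listed term.

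**6. Which mania-related events can reach the Akathisia category.** Protocol 5.2 makes exacerbation of the disease an adverse event only when its features are unusual or severe and not previously present, or not expected. It also asks for one unifying diagnosis where possible. What remains is unusual or severe exacerbation recorded as an overactivity symptom, and isolated symptom reports. Related symptoms are expected to be recorded as adverse events to some extent: protocol 4.1.1 allows lorazepam for treatment-emergent anxiety, agitation and insomnia.

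**The case against.** The strongest reply is that little depends on this grouping. It is descriptive and supportive, and the primary summaries are untouched. The SAP cites no classification standard, so the case for moving chorea and athetosis rests only on where it puts choreoathetosis. The events also stay identifiable by preferred term, since SAP 9.1 tabulates events by system organ class and preferred term for the sex, race, age and region subgroups. All of this stands, and it makes the point minor. It does not explain why the combined term and its components are separated.

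A reader might infer more than the documents support:

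- *That tardive dyskinesia is under-counted.* It is not. Tardive dyskinesia and dyskinesia are both named under Dyskinetic Events.
- *That under-counting will occur.* It requires at least one report of chorea or athetosis, and no rates are given.
- *That every psychomotor hyperactivity report is mania counted as akathisia.* Protocol 5.2 excludes most exacerbation from adverse event reporting, and such a report may be true akathisia.
- *That* hyportonia *could equally mean low muscle tone.* Alphabetical order favours *hypertonia*. The misprint may also have arisen when the PDF was read, and programming it literally is only a possibility.
- *That this grouping is the only EPS analysis.* Protocol Table 4.1-2 refers to EPS scales, the SAP section between 9.4 and 9.6 is redacted, and the list of summary tables (SAP 12) is not visible. Preferred terms within each category may already be planned.

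**Conclusion.** The point holds as a minor correction. By the SAP's own placement of choreoathetosis, the Dyskinetic category can be under-counted if chorea or athetosis is reported. The Akathisia category can include some mania-related events, within the limits set by protocol 5.2. Each affected subject is about 0.26 percentage points of one category if N = 384, or 0.57 if N = 175; how many there would be cannot be estimated from the documents. No primary result changes. The only item that could alter the count of subjects with any EPS term is the spelling, and only if the misprint is real and is programmed as printed.

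The conclusion assumes that the components of choreoathetosis belong with it, and that overactivity in this population is sometimes part of the illness.

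**What to change.** In SAP 9.1:

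1. List athetosis, chorea and choreoathetosis together under Dyskinetic Events, and also print the grouping as it now stands. The second table preserves comparability with the parent trials if they use the present lists, which the documents do not say. It also shows openly what the change does in an open-label trial.
2. Report akathisia alone beside the three-term Akathisia group.
3. Check *hyportonia* against the source file and the programmed list. If the misprint is real, correct it to *hypertonia*.

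The cost is an edit to the term list, a rerun and a few extra rows or one more table. No new data are needed. The one drawback, reduced comparability with trials summarised under the present lists, is met by printing both groupings.

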9.2 Clinical Laboratory Tests

Summary statistics for mean and mean change from baseline in the routine clinical laboratory measurements, prolactin concentrations, and HbA1c will be provided. Potentially clinically relevant results in laboratory tests will also be summarized.

Potentially clinically relevant laboratory measurement test results in the open-label treatment phase will be identified, summarized, and listed. Criteria for identifying laboratory values of potential clinical relevance are provided in Appendix 2.

9.2.1 Drug Induced Liver Injury (DILI)

Total bilirubin level should be checked for any subject with increased ALT or AST levels \geq three times the upper normal limits (ULN) or baseline.

- Reporting all DILI as SAE to the FDA based on Hy's Law:
 - \square AST or ALT > 3 x ULN or baseline and
 - \Box T Bili ≥ 2 x ULN or baseline

A separate incidence table will be provided for DILI cases, and the corresponding listing will be provided for Safety Sample during the open-label treatment phase.

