## 5.4 Potential Serious Hepatotoxicity

For a subject who experiences an elevation in AST or ALT that is  $\geq 3$  times the upper limit of normal (ULN), a total bilirubin level should also be evaluated. If the total bilirubin is  $\geq 2$  times the ULN, complete an IRE form with all values listed and also report as an AE on the ePlatform.

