Appendix 5 Criteria for Identifying Laboratory Values of Potential Clinical Relevance

Laboratory Tests	Criteria
Chemistry	
AST (SGOT)	≥ 3 x upper limit of normal (ULN)
ALT (SGPT)	≥ 3 x ULN
Alkaline phosphatase	≥ 3 x ULN
LDH	≥ 3 x ULN
BUN	≥ 30 mg/dL
Creatinine	$\geq 2.0 \text{ mg/dL}$
Uric Acid	
Men	$\geq 10.5 \text{ mg/dL}$
Women	$\geq 8.5 \text{ mg/dL}$
Bilirubin (total)	$\geq 2.0 \text{ mg/dL}$
CPK	≥ 3 x ULN
Prolactin	>ULN
Hematology	
Hematocrit	
Men	≤ 37 % and decrease of ≥ 3 percentage points from baseline
Women	≤ 32 % and decrease of ≥ 3 percentage points from baseline
Hemoglobin	• • • • • • • • • • • • • • • • • • • •
Men	≤ 11.5 g/dL
Women	≤ 9.5 g/dL
White blood count	$\leq 2.800 / \text{ mm}^3 \text{ or } \geq 16.000 / \text{ mm}^3$
Eosinophils	≥ 10%
Neutrophils	≤ 15%
Absolute neutrophil count	≤ 1,000/ mm 
Platelet count	$\leq 75,000/\mathrm{mm}^3\mathrm{or} \geq 700,000/\mathrm{mm}^3$
Urinalysis	
Protein	Increase of $\geq 2$ units
Glucose	Increase of $\geq 2$ units
Casts	Increase of ≥ 2 units
Additional Criteria	mercuse of E 2 mins
Chloride	$\leq$ 90 mEq/L or $\geq$ 118 mEq/L
Potassium	$\leq 2.5 \text{ mEg/L or } \geq 6.5 \text{ mEg/L}$
Sodium	$\leq$ 126 mEq/L or $\geq$ 156 mEq/L
Calcium	$\leq 8.2 \text{ mg/dL or} \geq 12 \text{ mg/dL}$
Glucose	2 of a may do of a 12 may do
Fasting	≥ 100 mg/dL
Non-Fasting	≥ 200 mg/dL
Total Cholesterol, Fasting	≥ 240 mg/dL
LDL Cholesterol, Fasting	≥ 160 mg/dL
HDL Cholesterol, Fasting	E 100 mg ou
Men Men	< 40 mg/dL
Women	< 50 mg/dL
Triglycerides, Fasting	≥ 150 mg/dL

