7.1 Baseline Definition

Baseline is defined as the last available measurement prior to the first dose of open-label IMP in the open-label treatment phase.

[figure not shown]

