Appendix 2 Criteria for Identifying Laboratory Values of Potential Clinical Relevance

Laboratory Tests	Criteria	
Chemistry		
AST (SGOT)	\geq 3 x upper limit of normal (ULN)	
ALT (SGPT)	$\geq 3 \times ULN$	
Alkaline phosphatase	\geq 3 x ULN	
Lactate dehydrogenase (LDH)	$\geq 3 \times ULN$	
Blood urea nitrogen (BUN)	$\geq 30 \text{ mg/dL}$	
Creatinine	$\geq 2.0 \text{ mg/dL}$	
Uric Acid	C	
Men	$\geq 10.5 \text{ mg/dL}$	
Women	$\geq 8.5 \text{ mg/dL}$	
Bilirubin (total)	$\geq 2.0 \text{ mg/dL}$	
Creatine phosphokinase (CPK)	$\geq 3 \times ULN$	
Prolactin	> ULN	
Hematology		
Hematocrit		
Men	\leq 37 % and decrease of \geq 3 percentage points from Baseline	
Women	\leq 32 % and decrease of \geq 3 percentage points from Baseline	
Hemoglobin		
Men	$\leq 11.5 \text{ g/dL}$	
Women	$\leq 9.5 \text{ g/dL}$	
White blood count	$\leq 2,800/\text{ mm}^3 \text{ or } \geq 16,000/\text{ mm}^3$	
Eosinophils	≥ 10%	
Neutrophils	≤ 15%	
Absolute neutrophil count	$\leq 1,000/{\rm mm}^3$	
Platelet count	$\leq 75,000/ \text{ mm}^3 \text{ or } \geq 700,000/ \text{ mm}^3$	
Urinalysis		
Protein	Increase of ≥ 2 units	
Glucose	Increase of ≥ 2 units	
Casts	Increase of ≥ 2 units	
Additional Criteria		
Chloride	\leq 90 mEq/L or \geq 118 mEq/L	
Potassium	$\leq 2.5 \text{ mEq/L or} \geq 6.5 \text{ mEq/L}$	
Sodium	$\leq 126 \text{ mEq/L or} \geq 156 \text{ mEq/L}$	
Calcium	$\leq 8.2 \text{ mg/dL or} \geq 12 \text{ mg/dL}$	
Glucose		
Fasting	$\geq 100 \text{ mg/dL}$	
Non-Fasting	$\geq 200 \text{ mg/dL}$	
Total Cholesterol, Fasting	$\geq 240 \text{ mg/dL}$	
LDL Cholesterol, Fasting	$\geq 160 \text{ mg/dL}$	
HDL Cholesterol, Fasting	-	
Men	< 40 mg/dL	
Women	< 50 mg/dL	
Triglycerides, Fasting	$\geq 150 \text{ mg/dL}$	

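### The SAP's DILI (Hy's Law) case rule adds an undefined *or baseline* alternative that Protocol 5.4 lacks, so the table can count subjects with all-normal values or drop protocol-defined cases, depending on how it is read

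*SAP*

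**What the plan says.** SAP 9.2.1 asks for a bilirubin check when ALT or AST reaches at least "three times the upper normal limits (ULN) or baseline". It then gives the case rule: "AST or ALT > 3 x ULN or baseline and" "T Bili ≥ 2 x ULN or baseline". A separate incidence table and a listing for the Safety Sample in the open-label phase rest on that rule. The same section carries the line "Reporting all DILI as SAE to the FDA based on Hy's Law".

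Protocol 5.4 has no baseline term. It asks for bilirubin when AST or ALT is at least 3 x ULN. If bilirubin is then at least 2 x ULN, the site must "complete an IRE form with all values listed and also report as an AE on the ePlatform".

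The criteria for potentially clinically relevant AST and ALT are also tied to ULN alone: "≥ 3 x upper limit of normal (ULN" in Protocol Appendix 5, and the same limit, "3 x upper limit of normal (ULN", in SAP Appendix 2.

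SAP 7.1 says: "Baseline is defined as the last available measurement prior to the first dose of open-label IMP". It sets no floor at ULN.

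**The concern.** Nothing visible in the SAP says whether exceeding either multiple is enough, whether baseline takes over from ULN when baseline is raised, or why the rule departs from the protocol. The SAP is explicit about such things elsewhere. Section 9.2.2 pairs baseline categories with post-baseline categories, and the hematocrit criterion in Appendix 2 joins a limit and a change from baseline with *and*.

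The two natural readings err in opposite directions. One admits subjects with nothing abnormal. The other raises the bar for subjects who start high. Two competent programmers could deliver different counts from the same data, and neither count need match the cases that sites report under Protocol 5.4. Safety is the purpose of this trial, and when cases are rare one false or missing case changes what the table conveys.

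**Working it through.** The plan states no figure for this rule, so there is none to reproduce. The check applies each version of the rule to illustrative subjects.

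**Rules**, with a and b the on-treatment ALT (or AST) and bilirubin, a0 and b0 the baselines, all in multiples of ULN:

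- Protocol 5.4: a ≥ 3 and b ≥ 2.
- Either-multiple reading of SAP 9.2.1: (a > 3 or a > 3·a0) and (b ≥ 2 or b ≥ 2·b0).
- Replacement reading: a > 3·max(1, a0) and b ≥ 2·max(1, b0).

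**Illustrative subjects** (assumed values):

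| ALT, x ULN | Bilirubin, x ULN | Protocol 5.4 | Either multiple | Replacement |
|---|---|---|---|---|
| 0.25 to 0.80 | 0.35 to 0.75 | no | **yes** | no |
| 1.5 to 4.0 | 0.6 to 2.5 | yes | yes | **no** (needs > 4.5) |
| 0.6 to 4.0 | 1.3 to 2.4 | yes | yes | **no** (needs ≥ 2.6) |
| 0.6 to 3.0 | 0.6 to 2.0 | yes | yes | **no** (3.0 is not > 3) |
| 1.0 to 3.0 | 0.6 to 2.0 | yes | **no** | **no** |
| 0.6 to 4.0 | 0.6 to 2.5 | yes | yes | yes |

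**When all values can be normal under the either-multiple reading.** Three times baseline must lie below ULN, so a0 < 1/3. Twice baseline bilirubin must not exceed ULN, so b0 ≤ 1/2.

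- With assumed ULNs of 40 U/L and 1.2 mg/dL, the limits are 40/3 = 13.3 U/L and 1.2/2 = 0.60 mg/dL.
- Over assumed ULNs of 30 to 55 U/L, the ALT limit is 10.0 to 18.3 U/L.
- Over assumed ULNs of 1.0 to 1.3 mg/dL, the bilirubin limit is 0.50 to 0.65 mg/dL.

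**In laboratory units, same assumed ULNs.** The protocol needs ALT ≥ 3 × 40 = 120 and bilirubin ≥ 2 × 1.2 = 2.4.

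- Over-count: ALT 12 to 37 exceeds 3 × 12 = 36 (37/12 = 3.08 x baseline, 37/40 = 0.93 x ULN). Bilirubin 0.3 to 0.6 equals 2 × 0.3 and is 0.5 x ULN. This is a SAP case with every value normal.
- Near-ULN baseline: 3 × 38 = 114 against 120, so the rules nearly agree.
- Under-count: ALT 72 to 160 is 160/40 = 4.0 x ULN but 160/72 = 2.2 x baseline. The replacement threshold is 3 × 72 = 216, or 5.4 x ULN. With bilirubin 0.8 to 2.4 (2.0 x ULN) this is a protocol case that the SAP would not count. At a baseline of 2 x ULN, the threshold is above 6 x ULN.

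**Raised baselines can occur.** Protocol 3.7.3.2 makes AST or ALT exclusionary at screening only above 2 x ULN and gives no numeric bilirubin limit. Per Table 3.7-1, a rollover subject's baseline is the Day 21 visit of the double-blind trial, and the SAP says only rollover subjects were enrolled.

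**Strict against non-strict inequality.** SAP 9.2.1 uses ≥ in its lead sentence and > in the case rule; the protocol uses ≥. Under the either-multiple reading this bites only at exactly 3.0 x ULN with baseline at or above ULN and no other qualifying transaminase. ALT 120 with baseline 38 is caught (120 > 114); with baseline 40 it is missed.

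**Reporting text.** SAP 9.2.1 speaks of reporting every DILI case as an SAE. Protocol 5.1 and 5.3 list potential serious hepatotoxicity as its own immediately reportable type alongside SAEs, and 5.4 asks for the IRE form plus an AE entry. A case may still meet a seriousness criterion under 5.1, but the texts are not aligned.

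**The case against.** The strongest reply is about consequence. SAP 9.2 lists and summarises results flagged by Appendix 2, which catches AST or ALT ≥ 3 x ULN and total bilirubin ≥ 2.0 mg/dL. Over bilirubin ULNs of 1.0 to 1.3 mg/dL, 2 x ULN is 2.0 to 2.6 mg/dL, so every Protocol 5.4 case would carry both flags, and Protocol 5.4 also requires an AE entry. This stands: the component values do not vanish. What is missing is any visible output that applies the combined ULN-only rule, and a case dropped under the replacement reading would be absent from the DILI listing as well as the table.

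Second, nothing in 9.2.1 states the replacement reading, and under the either-multiple reading the SAP rule contains the protocol rule except at exactly 3.0 x ULN. That is correct, but it leaves the over-count, which needs no special interpretation. The over-count is narrow: low-normal baselines, a tripling and a doubling, with scheduled post-baseline chemistry only at Week 12 and Week 26/ET. The listing would also expose an all-normal subject, but the incidence would already include that subject.

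Third, Protocol 5.4 is a site-reporting trigger, and Protocol 7.6 leaves details of safety analyses to the SAP. A broader screen is therefore permissible, but it must say how it works, and this one is labelled Hy's Law. Fourth, parts of the SAP are redacted, including conventions and the table list, so an explanation there cannot be excluded; 9.2.1 points to none. Fifth, the protocol requires medical monitor permission to enrol after a clinically significant screening result. That is a control on raised bilirubin, though not a limit. The inequality and SAE points are minor; the strict sign could even be an artefact of text extraction.

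**Conclusion.** The concern holds. As written, the rule counts a subject with every liver value normal as a DILI case if either multiple suffices, and drops protocol-defined cases if baseline replaces a raised ULN. Each direction is conditional on the reading; apart from the exact 3.0 x ULN edge, no single one of these readings produces both errors. The results in multiples of ULN need no reference range; the figures in U/L and mg/dL rest on the assumed ULNs. The documents give no distribution of baseline liver tests, so no frequency of misclassification can be given. The harm is limited to one supplementary descriptive table and its listing; the primary analysis of AE frequency and severity does not use this rule. It should be fixed before the table is programmed.

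**What to change.** Define the cases in the SAP 9.2.1 table and listing by the Protocol 5.4 thresholds, AST or ALT ≥ 3 x ULN with total bilirubin ≥ 2 x ULN, and delete *or baseline* from that definition. If an analysis for raised baselines is wanted, add it as a separate, labelled output with an explicit rule for how baseline and ULN combine. Reconcile the SAP's sentences on the bilirubin check and on SAE reporting with Protocol 5.1, 5.3 and 5.4. The cost is a few lines of SAP text and one table and listing specification; no new data are needed.

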9.2.2 Metabolic Change

In addition to mean change from baseline, incidence of treatment emergent significant changes in fasting lipids, fasting glucose, and metabolic syndrome will be summarized by parent study treatment group for rollover subjects and overall using the following criteria.

Criteria for Treatment-Emergent Significant Change in Lipids and Glucose					
LAB PARAMETER	LAB PARAMETER BASELINE ¹ ANYTIME POST BASELINE				
LDL Direct, Fasting	Borderline 100-<160	High >=160			
(MG/DL)	Normal/Borderline < 160	High >=160			
	Normal <100	Borderline/High >=100			
	Any Value	Increased >=30			
HDL Cholesterol, Fasting	Normal >=40	Low <40			
(MG/DL)	Any Value	Decreased >=20			
Triglycerides, Fasting	Normal <150	High 200-<500			
(MG/DL)	Borderline 150-<200	High 200-<500			
	Normal/Borderline <200	High 200-<500			
	Normal <150	Borderline/High/Very High >=150			
	Any Value	Increased >=50			
Glucose Fasting, Serum	Normal <100	High >=126			
(MG/DL)	Impaired 100-<126	High >=126			
	Normal/Impaired <126	High >=126			
	Any Value	Increased >=10			

¹ BASELINE IS DEFINED AS THE LAST AVAILABLE MEASUREMENT PRIOR TO THE FIRST DOSE OF OPEN-LABEL IMP IN THE OPEN-LABEL TREATMENT PHASE

Criteria for Treatment-Emergent Metabolic Syndrome			
DESCRIPTION	ANYTIME POST BASELINE ¹		
Central Obesity	Waist Circumference >=102cm(MALE), >=88cm (FEMALE)		
Dyslipidemia	Triglycerides >= 150mg/dl		
Dyslipidemia	HDL < 40mg/dl (MALE), <50mg/dl (FEMALE)		
Supine Blood Pressure	Systolic>=130mmHg and Diastolic>=85mmHg		
Glucose Fasting, Serum	>=100mg/dl		
Metabolic Syndrome	Met 3 Or More of the Above Criteria at a Visit		

¹ BASELINE IS DEFINED AS THE LAST AVAILABLE MEASUREMENT PRIOR TO THE FIRST DOSE OF OPEN-LABEL IMP IN THE OPEN-LABEL TREATMENT PHASE

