Appendix 1 Criteria for Identifying Vital Signs of Potential Clinical Relevance

Variable	Criterion Value ^a	Change Relative to Baseline ^a	
Heart Rate ^b	> 120 bpm < 50 bpm	≥ 15 bpm increase ≥ 15 bpm decrease	
Systolic Blood Pressure ^b	> 180 mmHg < 90 mmHg	≥ 20 mmHg increase ≥ 20 mmHg decrease	
Diastolic Blood Pressure ^b	> 105 mmHg < 50 mmHg	≥ 15 mmHg increase ≥ 15 mmHg decrease	
Orthostatic Hypotension	≥ 20 mmHg decrease in systolic blood pressure and a ≥ 25 bpm increase in heart rate from supine to sitting/standing	Not Applicable (baseline status not considered)	
Weight	-	≥ 7% increase ≥ 7% decrease	

^a In order to be identified as potentially clinically relevant, an on-treatment value must meet the "Criterion Value" and also represent a change from the subject's baseline value of at least the magnitude shown in the "Change Relative to Baseline" column.

^b As defined in "Supplementary Suggestions for Preparing an Integrated Summary of Safety Information in an Original NDA Submission and for Organizing Information in Periodic Safety Updates," FDA Division of Neuropharmacological Drug Products draft (2/27/87).

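### The metabolic-syndrome blood-pressure component needs systolic and diastolic pressure to be raised together; no reason is given, and compared with an either-pressure rule it can only lower the count.

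*SAP*

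**What the plan says.** SAP 9.2.2 lists five components: waist circumference, triglycerides ("Triglycerides >= 150mg/dl"), HDL, supine blood pressure and fasting glucose. The blood-pressure row reads "Systolic>=130mmHg and Diastolic>=85mmHg". A subject has the syndrome when the last row is satisfied: "Met 3 Or More of the Above Criteria at a Visit". The use is descriptive: incidence of "metabolic syndrome will be summarized by parent study treatment group for rollover subjects and overall using the following criteria".

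This is current SAP text, and no visible footnote qualifies the row. The visible protocol text defines no metabolic syndrome that could override it.

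**The concern.** A component labelled as blood pressure would ordinarily be expected to respond when either pressure is high. Here a subject at 175/84 misses by 1 mmHg of diastolic pressure, and one at 128/100 misses by 2 mmHg of systolic pressure.

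No other categorical output catches these readings. In SAP Appendix 1 the upper limits are 180 mmHg systolic and 105 mmHg diastolic, each with a required change from baseline, so neither reading is flagged there. They would enter only the summaries of change in vital signs.

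Safety and tolerability are the trial's only stated objective, and the protocol's rationale is long-term safety. A stricter definition than intended would make one prespecified metabolic safety incidence look lower than an either-pressure count.

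**Working it through.** **1. How the documents treat the two pressures**

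- SAP Appendix 1 gives each pressure its own row and limits: systolic "> 180 mmHg < 90 mmHg", diastolic "> 105 mmHg < 50 mmHg". Either can flag a subject alone.
- Protocol exclusion 16 takes diastolic pressure above 95 mmHg alone as uncontrolled hypertension, and joins the systolic and diastolic falls in orthostatic hypotension with *and/or*. It stands under the de novo heading and the SAP says no de novo subjects were enrolled, so it shows drafting practice only.
- In the SAP 9.2.2 syndrome table itself, triglycerides and HDL are separate rows, each scoring alone.
- SAP 9.4 uses a loose *and* in its QTc labels for men and women, but the adjacent criteria text says *or*. The blood-pressure row has no such clarification, so a programmer would code the joint condition.

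**2. Direction (exact)**

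Let S and D be 1 if systolic and diastolic pressure are raised, and K the number of the other four components met. The syndrome requires K + B ≥ 3, where B = S × D under *and*, and B = max(S, D) under *or*.

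The rules give a different B only when S + D = 1. The classification then differs only when K + 0 < 3 and K + 1 ≥ 3, that is, K = 2. Of the 2^6 = 64 patterns, C(4,2) × 2 = 12 move to syndrome under *or*, and none moves the other way. With K = 3 or 4 the subject is counted under both rules.

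**3. Size at component level (assumed inputs)**

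The documents state no blood-pressure distribution and no syndrome rate, so there is no figure of the plan's own to reproduce. Assume bivariate normal supine pressures: systolic mean 120-128, SD 12-15; diastolic mean 76-80, SD 8-10; correlation 0.6-0.8.

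Formulas: P(either) = P(S) + P(D) − P(both); share missed = 1 − P(both)/P(either).

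One example, with systolic 122 (SD 15), diastolic 78 (SD 10) and correlation 0.7:
- P(S) = P(Z ≥ 8/15) = 0.297; P(D) = P(Z ≥ 7/10) = 0.242; P(both) = 0.164.
- P(either) = 0.297 + 0.242 − 0.164 = 0.375.
- Share missed = 1 − 0.164/0.375 = 56%.

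Over the whole assumed range, *and* flags about 7-27% of subjects and *or* about 24-53%. The share missed is about 44-77% of subjects with at least one raised pressure.

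**4. Size at syndrome level (further assumptions)**

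Let each of the other four components have prevalence q, independent of each other and of blood pressure. Then P(syndrome) = P(K ≥ 3) + P(K = 2) × P(B = 1). Continuing the example with q = 0.35:
- P(K = 2) = 6 × 0.35² × 0.65² = 0.3105.
- P(K ≥ 3) = 4 × 0.35³ × 0.65 + 0.35⁴ = 0.1265.
- *And*: 0.1265 + 0.3105 × 0.1636 = 0.177.
- *Or*: 0.1265 + 0.3105 × 0.3752 = 0.243.
- Loss: (0.243 − 0.177)/0.243 = 27% of either-pressure cases.

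The syndrome-level range was run on a slightly different grid: systolic mean 118-126, SD 12-15; diastolic mean 75-81, SD 8-10; correlation 0.5-0.7; q 25-45%.

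| Quantity | *and* | *or* |
|---|---|---|
| Component met | 5-25% | 20-53% |
| Syndrome | 6-33% | 9-44% |

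The loss is 16-52% of either-pressure cases (median about 32%). If all of the roughly 384 planned subjects were assessed on all five components, that would be about 11-48 subjects.

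**The case against.** The best defence is that the joint rule may be deliberate. The table gives separately scored items separate rows, yet puts both pressures in one row. Joint rules also occur elsewhere: Appendix 1 requires a limit and a change from baseline, and its orthostatic row requires a systolic fall with a heart-rate rise. This stands as a reason to allow the sponsor to justify the rule. It supplies no rationale, and the visible SAP offers none.

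Several stronger readings are tempting but not supported:

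- *The SAP contradicts itself.* A reader might infer this from Appendix 1. That appendix is a variable-by-variable outlier screen with other limits and another purpose. It shows inconsistent handling, not a formal contradiction.
- *The rule is wrong against a standard definition.* The SAP cites no source for its criteria. The undercount is therefore relative to an either-pressure rule.
- *Most syndrome cases are missed.* The 44-77% concerns the component and has as its denominator subjects with at least one raised pressure. The syndrome-level loss is smaller because it needs exactly two other components.
- *The reported incidence is biased towards safety overall.* The table is headed treatment-emergent but lists only post-baseline criteria, with no visible requirement to be syndrome-free at baseline. That could push the count up, so the net direction is unknown.

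The reach is also limited. The primary endpoint is adverse events, there are no secondary endpoints, and this summary carries no test. After baseline, laboratory tests are scheduled at Weeks 12 and 26/early termination, and waist only at Week 26/early termination. All five components are therefore scheduled together only at that last visit.

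**Conclusion.** The point holds as a definitional weakness in one descriptive safety table. Two parts are exact: every subject with exactly one raised pressure fails the component, and the joint rule can never count more syndrome cases than an either-pressure rule.

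The size is illustrative. It rests on normality and on assumed means, SDs and correlations; the syndrome-level figure also rests on assumed prevalences, independence of the components and complete measurement. Real components are likely to be correlated, which would change it. The adverse-event analysis and the sample size are unaffected. The change should be made, but the trial's main conclusions do not depend on it.

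**What to change.** In the SAP 9.2.2 table and the program, make the blood-pressure row systolic ≥130 mmHg *or* diastolic ≥85 mmHg. If the joint condition is intended, say why in the SAP and report the either-pressure incidence beside it.

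The cost is one word in the table and the matching program line, or one extra row if both versions are reported. Supine pressures are already collected, so no new data are needed. The reported incidence may be somewhat higher.
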